4. TREATMENTS

4.1 TREATMENTS TO BE ADMINISTERED

Patients will be allocated to the following treatments according to the order they enter the study site, while be assigned to Tiotropium+Olodaterol FDC treatment group:

Tiotropium + olodaterol FDC (5 µg/ 5 µg) solution for inhalation

During the entire 3-week treatment period, the patients inhale 2 puffs from the RESPIMAT inhaler, once a day, in the morning.

The investigational products will be provided by Boehringer Ingelheim.

4.1.1 Identity of BI investigational products and comparator product

Table 4.1.1: 1 Test product:

Substance:	Tiotropium + olodaterol fixed-dose combination
Pharmaceutical formulation:	Solution for inhalation
Source:	Boehringer Ingelheim Pharma GmbH & Co. KG
Unit strength:	2.5µg/ 2.5µg per actuation (tiotropium/olodaterol)
Posology	2 inhalations once daily (AM dosing)
Route of administration:	Oral inhalation via RESPIMAT inhaler (A5)

4.1.2 Method of assigning patients to treatment groups

Upon signing informed consent, patients will be assigned a unique patient number using the remote data capture (RDC) system.

Patients are allocated to treatment groups at Visit 2. After assessment of all in- and exclusion criteria, each eligible patient will be assigned the lowest available medication number at the time of treatment. The 16 medications, medication number starting from the lowest, contain Tiotropium + olodaterol fixed-dose combination. Note that the medication number is different from the patient number (the latter is assigned at trial entry). Site personnel will enter the medication number on the eCRF. See [Section 4.1.6](#) for details on packaging and labelling.

4.1.3 Selection of doses in the trial

Tiotropium + olodaterol FDC (5 µg/ 5 µg) will be the submitted doses in China. These doses are included in the trial in order to assess PK in Chinese patients with COPD as required by CFDA.

4.1.4 Drug assignment and administration of doses for each patient

Dispensing of trial medication

Trial medication will be dispensed to the patient by the investigator/pharmacist. The amount of trial medication dispensed will be recorded on the drug accountability forms.

Priming of the RESPIMAT inhaler

Each newly assembled RESPIMAT inhaler has to be primed. Priming should **NOT** take place in the same room where the patient is inhaling trial medication nor where samples for PK analyses are drawn or processed (to avoid contamination of the environment). At Visit 2, priming should be performed by site personnel, and not by the patient himself. The inhaler should be primed by actuating it until an aerosol is visible plus three additional actuations. All priming actuations should be directed to the ground. For detailed priming instructions, please see the RESPIMAT inhaler handling instructions in [Appendix 10.2](#).

Once the cartridge is inserted into the Respimat inhaler, the shelf-life of the RESPIMAT with **trial** medication is 3 months. Once assembled, the shelf-life of the RESPIMAT with **training** medication is also 3 months. Therefore it is important to ALWAYS enter the date of the cartridge insertion on the medication label of the RESPIMAT immediately after the cartridge is inserted.

Testing of the MDI (rescue medication)

Before using for the first time, one actuation should be released into the air to make sure the device is working.

Trial medication administration at clinic visits

Detailed written instructions and training for the use of the RESPIMAT inhaler will be given to the patient at Visit 1 and the patient will inhale from the training device. (See [Appendix 10.2](#)). The investigator or qualified study personnel will observe the inhalation procedure and will reinforce a correct inhalation technique. At Visit 2, detailed instructions on the use of the device will be repeated, but the patient will not inhale from the training device. Patients inhale the first dose of trial medication at Visit 2.

The utmost care should be taken to ensure that the study medication is not taken prior to coming to the site at Visit 3 and Visit 4. At Visit 2 (after all assessment completion), Visit 3 and Visit 4 puffs of the study medication from the assigned RESPIMAT inhaler will be self-administered by the patient under the direct supervision of the investigating physician or deputy. Gloves must be worn and discarded immediately after the priming to avoid contamination of the PK samples to be taken and processed subsequently. The patient should not be present while priming takes place. Inhalation should **NOT** take place in the same room where samples for PK analyses are drawn or processed (to avoid contamination of the environment). Patient should inhale his/her medication in an isolated area from other patients (to avoid contamination of the environment).

Trial medication administration at home

Patients will receive two medication boxes; only one RESPIMAT inhaler should be ready for use (= cartridge inserted and primed). Once a cartridge is inserted in a RESPIMAT inhaler, the shelf-life is limited.

Each morning except on the days of a clinic visit, *two* puffs of the trial medication from the assigned RESPIMAT inhaler will be self-administered by the patient.

Patients have to be instructed that for the three days preceding the days with PK sampling, the appropriate dose of study medication must be self-administered within ± 5 min of time of drug administration at Visit 2 AND between 7:00 AM and 10:00 AM in order to avoid influence on the data collected on the Visits 3 and 4.

If the patient forgot to inhale the study medication within the specified time window, the patient is allowed to administer the dose until 12:00 PM (noon). After 12:00 PM the patient should skip the dose and take the next dose at the next scheduled time the following day and make a note of the missed dose in his/her medication worksheet.

RESPIMAT inhaler return

The RESPIMAT inhalers dispensed for the treatment period can be used for approximately 30 days each. All used and unused trial medication must be returned at Visit 4 by the patient. Any RESPIMAT inhaler that has been reported as malfunctioning by a patient or investigator will be returned to the BI for investigation. See the ISF for specific instructions and for details regarding drug accountability requirements. Details of the procedure for the return of malfunctioning inhalers are provided in [Appendix 10.3](#).

4.1.5 Blinding and procedures for unblinding

4.1.5.1 Blinding

Not applicable since this is an open-label trial.

4.1.5.2 Unblinding and breaking the code

Not applicable since this is an open-label trial.

4.1.6 Packaging, labelling, and re-supply

All trial medication will be contained in individual RESPIMAT treatment boxes identified with the trial number and a medication number. The boxes will have a two-part tear-off label. One part of each tear-off label will remain on the box, and the other part will be attached to a special drug dispensing log which will be part of the ISF. Examples of the labels are provided in the ISF.

The investigator or designee should fill out the following information on the medication label prior to dispensing the medication to the patient:

- date of cartridge insertion (RESPIMAT inhaler only; should be entered at time of cartridge insertion)

For details of packaging and the description of the label, see the ISF.

RESPIMAT treatment box

The RESPIMAT treatment box will contain one RESPIMAT inhaler plus one drug-filled cartridge and contains sufficient medication for 30 days of treatment.

The RESPIMAT inhaler will lock after 60 actuations have been administered and will no longer

actuate any medication.

Medication dispensing

Two boxes are packed in one outer box with medication number. The one box should be used for the treatment period and the other box is for reserve.

The one RESPIMAT inhaler will be primed by the site staff (See [Section 4.1.4](#)) used to dose the patient at inhalation at the end of Visit 2, as well as continued to be used at home until Visit 4. The other RESPIMAT for reserve medication is to allow the patient the flexibility of not having to return to the site immediately to replace a lost or malfunctioning RESPIMAT inhaler.

NOTE: The RESPIMAT and drug-filled cartridge that is not yet in use by the patient should NOT be assembled prior to leaving the site. The patient must assemble and prime the reserve device at home if needed (See [Appendix 10.2](#)).

The date of cartridge insertion should be entered (label of RESPIMAT inhaler only) at time of cartridge insertion only, i.e. for the first RESPIMAT inhaler this is entered by site staff (at Visit 2), for the second RESPIMAT inhaler the patient is advised to do so when assembling this device at home during the treatment period.

Supplies other than treatment medication

BI will provide the following open-label supplies:

- RESPIMAT inhalers, placebo cartridges for training purposes. One training device will be used for several patients. The training RESPIMAT can be used until 3 months after first insertion of the cartridge or until the device is empty. The date of the cartridge insertion should be entered on the medication label of the RESPIMAT immediately after the cartridge is inserted.
- Salbutamol MDI inhalation aerosol (100 µg per actuation) for use as rescue medication during screening, treatment and follow-up periods (Visit 0 to Visit 4). It will also be used for reversibility testing at Visit 1. Salbutamol will be purchased at site and dispensed to the patient at site visits as needed.
- Ipratropium bromide will be purchased at site and provided to be dispensed at the discretion of the investigator for use by patients on long acting anticholinergics (LAMA) during the 3-week washout period of LAMA preceding Visit 2.

For details of packaging and the description of the label, refer to the ISF.

4.1.7 Storage conditions

All clinical trial supplies, which will be provided by the sponsor, must be stored in a secure, limited access storage area under the storage conditions defined on the label and may only be dispensed to patients according to protocol. A temperature log must be maintained at the site to make certain that the drug supplies are stored at the correct temperature. If the storage conditions are found to be outside the specified range, immediately contact the CML.

Regarding to the drug which will be used by patient at home, a patient diary will be provided to patient which including the drug storage temperature record.

Further details are provided in the labels, a sample of which will be part of the ISF.

4.1.8 Drug accountability

The Investigator or Pharmacist or investigational drug storage manager will receive the investigational drugs delivered by the Sponsor when the following requirements are fulfilled:

- Approval of the trial protocol by the IRB / ethics committee,
- Availability of a signed and dated clinical trial contract between the Sponsor and the head of the investigational site,
- Approval/notification of the regulatory authority, e.g. competent authority,
- Availability of the curriculum vitae of the principal Investigator,
- Availability of a signed and dated clinical trial protocol
- Availability of the proof of a medical license for the principal Investigator

The Investigator or Pharmacist or investigational drug storage manager must maintain records of the product's delivery to the trial site, the inventory at the site, the use by each patient, and the return to the Sponsor or alternative disposal of unused products.

These records will include dates, quantities, batch / serial numbers, expiry ('use- by') dates, and the unique code numbers assigned to the investigational product and trial patients. The Investigator / Pharmacist / investigational drug storage manager will maintain records that document adequately that the patients were provided the doses specified by the CTP and reconcile all investigational products received from the Sponsor. At the time of return to the Sponsor or appointed CRO, the Investigator / Pharmacist / investigational drug storage manager must verify that all unused or partially used drug supplies have been returned by the clinical trial patient and that no remaining supplies are in the Investigator's possession.

4.2 CONCOMITANT THERAPY, RESTRICTIONS, AND RESCUE TREATMENT

The investigator must record all medication used by the patient for the three months preceding the Screening Visit (Visit 1) and throughout the trial, on the eCRF. This record will include the name of the medication, the total daily dose, route of administration, dates when medication was started and stopped, and the indication for medication usage.

4.2.1 Rescue medication, emergency procedures, and additional treatments

4.2.1.1 Rescue medication

Administration of rescue medication can occur at any point during the trial as deemed necessary by the patient or the investigator. Open label salbutamol MDI (100 µg per puff) will be provided as rescue medication by Site; the salbutamol MDI purchased at site is allowed for rescue medication use.

4.2.1.2 Emergency procedures

There are no special emergency procedures to be followed.

4.2.1.3 Additional treatments

Medications Allowed to Control Acute Exacerbations as Medically Necessary during the Treatment Period:

- Salbutamol inhalation aerosol from MDI for p.r.n. use provided by Site.

- Temporary increases in the dose or addition of oral steroids are allowed during the treatment portion of the study. Pulmonary function testing should not occur within seven days of the last administered dose of an increase or addition of oral steroids. Pulmonary function testing may be postponed up to 14 days to meet this restriction. Subsequent visits will be scheduled according to the patient's regular schedule.
- Temporary additions of theophylline preparations are allowed during the treatment portion of the study. Pulmonary function testing should not occur within seven days of the last dose. Pulmonary function testing may be postponed up to 14 days to accommodate this restriction. Subsequent visits will be scheduled according to the patient's regular schedule.
- The use of antibiotics is not restricted and may be prescribed as medically necessary for exacerbations and / or infections. If antibiotics are prescribed for a respiratory infection prior to pulmonary function testing days, the testing will be postponed for at least two days but not more than seven days after the last dose is given. Subsequent visits will be scheduled according to the patient's regular schedule. There are no special emergency procedures to be followed.

4.2.2 Restrictions

4.2.2.1 Restrictions regarding concomitant treatment

The following [Table](#) provides an overview of permitted and restricted medication.

Table 4.2.2.1: 1 Permitted Medications and Medication Restrictions

Drug Class	Sub-class	Prior to study	Study Period		
			Screening Period	Treatment Period	Follow up Period
Corticosteroids⁴	Inhaled corticosteroids (stabilized 6 wks prior to V1)	Permitted	Permitted	Permitted	Permitted
	Oral corticosteroids [≤10 mg prednisone per day or ≤20 mg prednisone every other day (or equivalent); stabilized 6 wks prior to V1]	Permitted	Permitted	Permitted	Permitted
	Injected corticosteroids – local administration (for treatment of e.g. bursitis)	Permitted	Permitted	Permitted	Permitted
β-adrenergics	Inhaled short-acting β-adrenergics	Permitted ¹	Rescue ¹	Rescue ¹	Permitted
	Inhaled long-acting β-adrenergics (bid) (e.g. formoterol / salmeterol)	Permitted (w.o. 48 hrs prior to V1)	NOT permitted	NOT permitted	Permitted
	Inhaled long-acting β-adrenergics (qd) (e.g. indacaterol, olodaterol)	Permitted (w.o. 1 week prior to V1)	NOT permitted (w.o. 3 wks prior to [visit 2])	Study medication	Permitted
	Oral and patch beta-adrenergics	Permitted (w.o. 4 wks prior to V1)	NOT permitted	NOT permitted	Permitted
	Beta blockers (cautionary statement, Section 3.3.3 ; stabilized 6 wks prior to V1)	Permitted	Permitted	Permitted	Permitted

Table 4.2.2.1: 1 Permitted Medications and Medication Restrictions (cont.)

Drug Class	Sub-class	Prior to study	Study Period		
			Screening Period	Treatment Period	Follow up Period
Anticholinergics	Short-acting anticholinergics (e.g. inhalation aerosol, nasal spray)	Permitted ¹	Permitted until [visit 2] (w.o. 8 hrs prior to [visit 2])	NOT permitted	Permitted
	Long-acting anticholinergics (bid / qd) (e.g. tiotropium, aclidinium, glycopyrronium, umeclidinium)	Permitted (w.o. 1 week prior to V1)	NOT permitted (w.o. 3 wks prior to [visit 2])	Study medication	Permitted
Combinations	ICS / long-acting β-adrenergics (bid) (switch to ICS mono-product, no change to steroid dose, at least 48 hrs prior to V1)	Permitted ¹	NOT permitted	NOT permitted	Permitted
	ICS / long-acting β-adrenergics (qd) (switch to ICS mono-product, no change to steroid dose + LABA bid, at least 3 weeks prior to V1) (e.g. fluticasone+vilanterol)	Permitted ¹	NOT permitted	NOT permitted	Permitted
	ICS / short-acting β-adrenergics (switch to ICS mono-product, no change of steroid dose, at least 8 hrs prior to V1)	Permitted ¹	NOT permitted	NOT permitted	Permitted
	Short-acting anticholinergic / short-acting β-adrenergics	Permitted (w.o. 8 hrs prior to V1)	NOT permitted	NOT permitted	Permitted
	Long-acting anticholinergics / long-acting β-adrenergics³ (e.g. glycopyrronium+indacaterol, umeclidinium+vilanterol)	Permitted (w.o. 1 week prior to V1)	NOT permitted (w.o. 3 wks prior to [visit 2])	Study medication	Permitted

Table 4.2.2.1: 1 Permitted Medications and Medication Restrictions (cont.)

Drug Class	Sub-class	Prior to study	Study Period		
			Screening Period	Treatment Period	Follow up Period
Miscellaneous	Other investigational drugs (*see exclusion criterion #xx)	NOT permitted*	NOT permitted	NOT permitted	NOT permitted
	Cromolyn sodium / nedocromil sodium (* if prescribed for non-asthma condition)	Permitted*	Permitted*	Permitted*	Permitted*
	Antihistamines, antileukotrienes (* if prescribed for non-asthma condition)	Permitted*	Permitted*	Permitted*	Permitted*
	Methylxanthines/Theophyllines (* if prescribed for non-asthma condition)	Permitted*1	Permitted*1	Permitted*1	Permitted
	Mucolytics (*not containing bronchodilators; stabilized 6 wks prior to V1)	Permitted*	Permitted	Permitted	Permitted
	PDE-4 inhibitors (e.g. roflumilast)	NOT permitted2	NOT permitted	NOT permitted	NOT permitted

w.o.: wash out, V: Visit

- Refer to [Section 4.2.2.1](#) for washout period prior to PFTs.
Refer to [Section 4.2.1](#) for washout period prior to PFTs in case of treatment of a COPD exacerbation.
- Patients currently using PDE4-inhibitors (e.g. roflumilast) should not be enrolled and roflumilast should not be withdrawn for the purpose of enrolling in this study.
Patients who were using roflumilast in the past may be included if their last use was a minimum of 3 months prior to Visit 1. In the event a patient with prior use of roflumilast is enrolled, past medical records are required to support and document why and when roflumilast was stopped.
- Patients may be switched to bid LABA and / or short acting anticholinergic. Refer to Section 4.2.2.1 for washout period prior to PFTs
- Patients are not allowed to initiate nor change the dose of Inhaled corticosteroids and oral corticosteroids during the trial.

Medication restrictions for pulmonary function testing for reviewing eligibility of patient at Visit 1:

- At least an 8-hour washout of short-acting beta-adrenergic bronchodilators prior to Visit 1.
- At least an 8-hour washout of short-acting anticholinergic bronchodilators prior to Visit 1.
- At least a 1-week washout of long-acting anticholinergic bronchodilators prior to Visit 1.
- At least a 1-week washout of long-acting beta-adrenergic bronchodilators (q.d.) prior to Visit 1.
- At least a 48-hour washout of long-acting beta-adrenergic bronchodilators (b.i.d.) prior to Visit 1.
- The morning dose of inhaled steroids should not be taken in the 1-hour period prior to PFTs.
- At least a 24-hour washout of short-acting (b.i.d. or more frequent administration) theophylline preparations.
- At least a 48-hour washout of long-acting (q.d. administration) theophylline preparation.

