2.3 BENEFIT - RISK ASSESSMENT

The clinical trials conducted to date have shown tiotropium + olodaterol 5/5 µg to be a safe, well tolerated and efficacious combination therapy according to treatment guidelines in a moderate to very severe COPD patient population that included patients with concomitant cardiovascular diseases.

The observed incremental bronchodilator response for tiotropium + olodaterol 5/5 µg compared to the individual components translated into benefits that were meaningful to the patient, with improvements in several patient centred outcomes. As such, tiotropium + olodaterol 5/5 µg will be a valuable additional therapeutic option for patients with COPD, offering increased treatment benefit compared to the monotherapies with a comparable safety profile.

Based on the overall assessment of benefit to risk, the application for marketing authorization for tiotropium + olodaterol FDC was submitted in the EU and the US in May 2014, and then subsequently in several other countries, including Canada.

The trial design requires that all eligible patients complete a 3 to 4 week screening period in which LABAs and LAMAs are withdrawn prior to treatment. Site will provide open-label salbutamol (albuterol) as needed (PRN) rescue medication for all patients who have signed Informed Consent.

All patients will receive active treatment with tiotropium + olodaterol FDC (5 µg / 5 µg) during the treatment periods. There is no placebo comparator in this trial.

Patients receiving inhaled corticosteroids before enrolment will continue their treatment (or the inhaled corticosteroids component alone if taken as a fixed combination with bronchodilator) at the same equivalent dose and regimen during the study. The only medications that are excluded during the treatment period are anticholinergic and long-acting β-adrenergic other than the study drugs.

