3.3.4 Removal of patients from therapy or assessments

3.3.4.1 Removal of individual patients

An individual patient is to be withdrawn from the trial if any of the following criteria apply:

1. The patient withdraws consent, without the need to justify the decision.
2. The patient is no longer able to participate for medical reasons (e.g. pregnancy, surgery, adverse events, or other diseases), or contraindications for exercise testing have occurred.

3. Administrative reasons (protocol violations, persistent non-compliance).
4. Decision by Boehringer Ingelheim to discontinue one or all patients (e.g., new toxicological findings or SAEs invalidate the earlier positive benefit–risk assessment).

No patient should be discontinued from the trial for a protocol violation before discussion with the clinical monitor. In the event of a COPD exacerbation, please contact the CML / TCM to discuss the possibilities to re-schedule the clinic visits.

Data of patients who discontinue or withdraw prior to allocation will be entered in the trial database and will be listed. Data of patients who discontinue or withdraw after allocation must be documented with the reason for withdrawal in source document and must be recorded in the electronic case report form (eCRF). The data must be included in the trial database and must be reported.

See [Section 6.2.4](#) for procedures to be followed for patients prematurely terminating the trial.

Pregnancy

If a patient becomes pregnant during the trial the investigational product needs to be stopped and the patient should be followed up until birth or until termination of the pregnancy. The data of the patient will be collected and reported in the CTR until patient's last visit and any events thereafter will be reported in the BI drug safety database. See [Section 5.3.7](#) for detailed information on event reporting in case of pregnancy.

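### Section 4.2.1.3 allows oral steroids to be added or increased for an exacerbation in the treatment period, while footnote 4 of Table 4.2.2.1:1 forbids it

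*Protocol*

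**What the plan says.** Protocol Section 4.2.1.3 has a list headed "Medications Allowed to Control Acute Exacerbations as Medically Necessary during the Treatment Period". Its entry on oral steroids reads: "Temporary increases in the dose or addition of oral steroids are allowed during the treatment portion of the study".

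Table 4.2.2.1:1 gives the permitted and restricted medicines by study period. Its corticosteroid class is marked "Corticosteroids⁴", and the footnote behind that superscript reads: "Patients are not allowed to initiate nor change the dose of Inhaled corticosteroids and oral corticosteroids during the trial". Within the class, the oral row is marked as permitted in every period, but it describes maintenance use only: "Oral corticosteroids [≤10 mg prednisone per day or ≤20 mg prednisone every other day (or equivalent); stabilized 6 wks prior to V1".

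Section 2.3, in the benefit-risk narrative, touches the subject from another side: "The only medications that are excluded during the treatment period are anticholinergic" and long-acting beta-adrenergic drugs other than the study drugs. The sentence before it says that patients already on inhaled corticosteroids stay on an equivalent dose and regimen.

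SAP Table 6.2:1 lists use of a prohibited medicine as important protocol violation D1, found by manual review of concomitant therapies. Its exclusion column reads none.

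**The concern.** The footnote and Section 4.2.1.3 address the same act and give opposite instructions. A site that consults the table finds a ban on starting or raising an oral steroid. A site that consults Section 4.2.1.3 finds a permission. The event is one that the protocol expects could happen, since it sets out a treatment list for it.

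Two things are at stake. A site that follows the footnote could delay or withhold a treatment that the protocol allows elsewhere. And whoever reviews concomitant therapies for the SAP could code the same course as allowed therapy or as D1, depending on which text is taken as the rule.

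**Working it through.** The plan states no figure on this point, so the check compares the texts.

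| | Section 4.2.1.3 | Footnote 4 of Table 4.2.2.1:1 |
|---|---|---|
| Drug | oral steroids | inhaled and oral corticosteroids |
| Act | adding, or temporarily raising the dose | starting, or changing the dose |
| Period | treatment period | whole trial |
| Condition | acute exacerbation | none stated |
| Instruction | allowed | not allowed |

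**Step 1: overlap.** The treatment period is part of the trial, an addition is a start, and an increase is a dose change. The two rules therefore meet on oral steroids given for an exacerbation in the treatment period. They do not meet elsewhere. Section 4.2.1.3 gives no permission for inhaled steroids, or for screening or follow-up, and on inhaled steroids Section 2.3 agrees with the footnote.

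**Step 2: does any text resolve it?**
- The notes under the table do point to Section 4.2.1, but only "for washout period prior to PFTs in case of treatment of a COPD exacerbation". That pointer belongs to footnote 1, and the corticosteroid class carries only superscript 4.
- The oral steroid row contains no exception for an exacerbation.
- Section 3.3.4.1 says: "In the event of a COPD exacerbation, please contact the CML / TCM to discuss the possibilities to re-schedule the clinic visits". It deals with visit dates, not with steroids.
- The Section 2.3 sentence leaves corticosteroids off its list of excluded medicines, but says nothing about starting or changing them.
- Neither global amendment described in Section 11 touches these texts.

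No exception or order of precedence is stated.

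**Step 3: consequence in the analysis.** If the footnote governs, the course is a candidate for D1. If Section 4.2.1.3 governs, it is not. Since D1 has no exclusion attached, the patient stays in the treated set and D1 does not remove the patient from the PK set. Only the listing of violations changes.

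**Step 4: how often it could arise.** The documents give no exacerbation rate. As an assumption, take 0.5 to 1.5 exacerbations per patient-year.
- Exposure: 16 patients × 3/52 years = 0.923 patient-years.
- Expected exacerbations: 0.923 × 0.5 = 0.46, and 0.923 × 1.5 = 1.38.
- Chance of at least one (Poisson): 1 − exp(−0.46) = 0.37, and 1 − exp(−1.38) = 0.75.

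Under the assumed rates, 37% to 75% is an upper bound on the chance of meeting the conflict. It counts every exacerbation as steroid-treated, although Section 4.2.1.3 also lists salbutamol, theophylline and antibiotics. It also ignores that patients must first pass a screening period meant to confirm stability (Section 3.1).

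**The case against.** The best defence is that the specific rule overrides the general one. Section 4.2.1.3 concerns temporary changes for an acute event. The table is presented as an overview, and its steroid entries concern stable maintenance doses. On that reading only a cross-reference is missing.

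The reading is reasonable, but the documents do not state it. The footnote is worded without limit, and the nearby pointer to Section 4.2.1 serves another purpose. The steroid entry in Section 4.2.1.3 is itself tied to postponing pulmonary function tests, while the flow chart and Appendix 10.4 place those tests only at Visit 1, before treatment. A site could fairly doubt that the entry was adapted to this trial and rely on the table.

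A second defence is that the sponsor will be involved anyway. Section 3.3.4.1 sends the site to the monitors when an exacerbation occurs, and Section 8.7 provides for departures from the protocol for medically compelling reasons. Both make it less likely that treatment is withheld. Neither settles the rule: the first concerns rescheduling, and the second would treat the course as a departure that Section 4.2.1.3 says it is not.

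A reader might go further and infer that patients would be withdrawn as non-compliant, that steady-state profiles would be lost, and that the dropout allowance would be used up. The documents do not support that. Section 3.3.4.1 requires discussion with the clinical monitor before anyone is discontinued for a violation, and Section 7.7 provides for additional patients if dropout exceeds 25%.

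**Conclusion.** The contradiction is real and narrow. It covers starting or raising an oral steroid for an exacerbation in the treatment period, and nothing in either document resolves it. It should be corrected because it leaves a site with opposite instructions on acute care and leaves the D1 classification undefined.

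Its statistical size is small. The D1 entry, as written, excludes nobody, so the pharmacokinetic results do not depend on how such a course is coded. That conclusion assumes the entry is not changed before database lock.

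A reader might also infer that corticosteroids in general, or the whole trial, are affected, or that Section 2.3 sets a third rule. The texts do not bear this out: the permission covers only oral steroids in one period, and the Section 2.3 sentence is narrative that should be checked for agreement. The 37% to 75% figure is an upper bound on an assumed rate, and the verdict does not rest on it.

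**What to change.** Reconcile Section 4.2.1.3 and footnote 4 into one statement on oral steroids for an exacerbation in the treatment period, and use the same wording in both places. Which version holds is the sponsor's clinical decision. Check that the Section 2.3 sentence on excluded medicines agrees with it. In SAP Table 6.2:1, add a comment to D1 saying whether such a course counts as a violation, in line with the reconciled text.

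The cost is one sentence in a protocol amendment and one comment in the SAP table. No procedure, sample or analysis is added.
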